## 1. Glossary

Abbreviation	Definition
AE	Adverse Event
ADE	Adverse Device Effect
AHCL	Advanced Hybrid Closed Loop
AI	Artificial Intelligence
ASIC	Application Specific Integrated Circuit
BG	Blood Glucose
CEC	Clinical Events Committee
CFR	Code of Federal Regulations
CGM	Continuous Glucose Monitoring
CHO	Carbohydrate
CSII	Continuous Subcutaneous Insulin Infusion
DKA	Diabetic Ketoacidosis
DMC	Data Monitoring Committee
eCRF	Electronic Case Report Form
EIS	Electrochemical Impedance Spectroscopy
EOS	End of Study
ER	Emergency Room
FDA	United States Food and Drug Administration
FST	Frequent sample testing
GCP	Good Clinical Practice

Abbreviation	Definition
HCL	Hybrid Closed Loop
HCP	Health Care Provider
HIPAA	Health Insurance Portability and Accountability Act of 1996
IB	Investigator's Brochure
ICF	Informed Consent Form
IEC	Independent Ethic Committee
IFU	Instructions for Use
IRB	Institutional Review Board
IV	Intravenous
MC2	Medtronic Core Clinical Solutions
MDI	Multiple Daily Injection
NGSP	National Glycohemeglobin Standardization Program
OC-RDC	Oracle Clinical Remote Data Capture
PC	Personal Computer
PCL	Personalized Closed Loop
RF	Radio Frequency
SAE	Serious Adverse Event
SADE	Serious Adverse Device Events
SAP	Sensor Augmented Pump
SG	Sensor Glucose
SMBG	Self-Monitoring of Blood Glucose
TDD	Total Daily Dose
TLS	Transport Layer Security

Abbreviation	Definition
TS	Technical Support
TSH	Thyroid-stimulating hormone
UADE	Unanticipated Adverse Device Effect

Ascensia, the Ascensia Diabetes Care logo, and Contour are trademarks and/or registered trademarks of Ascensia Diabetes Care.

Humalog™\* is a registered trademark of Eli Lilly and Company.

NovoLog™\* is a trademark of Novo Nordisk A/S.

© 2020 Medtronic. All rights reserved. Medtronic, Medtronic logo and Further, Together are trademarks of Medtronic. TM\*Third party brands are trademarks of their respective owners.

All other brands are trademarks of a Medtronic company.

## 2. Synopsis

Title	Feasibility Study with Personalized Closed Loop (PCL)
Investigational Device Exemption (IDE) Number	G190301
Devices	
Feasibility 2: Investigational Devices
 

• Cloud-based Digital Twin Algorithm

• Cloud-based Meal Prediction Algorithm

• MiniMed™ 670G Insulin Pump, version 4.0 Tel-D (MMT-1740) – AHCL

• PCL Mobile Application- referred to as App in the protocol (MMT-TBD)

 
Feasibility 2: Non-Investigational/Exempt devices
 

• Guardian™ Link (3) Transmitter (MMT-7811)

• Guardian™ Sensor (3) Glucose Sensor (MMT-7020)- referred to as Guardian Sensor (3) throughout this protocol

• One-Press Serter (MMT-7512) - referred to as the Serter throughout this protocol

• Transmitter Charger (MMT-7715)

• Tester (MMT-7736L)

• Medtronic CareLink™ Personal Therapy Management Software for Diabetes (MMT-7333) -- referred to as CareLink™ Personal For Clinical Research software throughout this protocol; Class I exempt device

• CONTOUR® NEXT LINK 2.4 Blood Glucose Meter (MMT-1352)- referred to as the CONTOUR® NEXT LINK 2.4 study meter throughout this protocol

• Subject-owned Smartphone to accommodate Medtronic PCL Mobile App

Purpose	
The purpose of this study is to:
 

• Evaluate subject safety related to automated recommendations for device setting changes that are formulated by the Cloud-based Digital Twin algorithm and impact insulin delivery.

	

• Evaluate subject safety related to carbohydrate estimates for meals that are calculated by the Cloud-based Meal Prediction algorithm.

Objective(s)	The objective of the study is to collect device data to assist in the development of a Personalized Closed Loop (PCL) system.
	This is a single arm study comprised of a series of feasibility studies. Please see below:    Feasibility Study Part 2 (i.e. Feasibility 2): Feasibility 2 is the focus of the current protocol.  
Study Design	
This study may include up to 3 separate Cohorts of individuals, based on which algorithm is being studied:
 
Cohort A: The main purpose of this cohort is to test the Digital Twin insulin delivery algorithm adaptation (Feasibility 2 [REDACTED]) 
 
Cohort C: The main purpose of this cohort is to test a meal prediction algorithm (Feasibility 2 [REDACTED])
 
Study Phases
 
This study consists of one or more phases. See Table 1 for a Summary of phases for Feasibility 2.
 

• Phases may be repeated per sponsor direction

• Phases in different cohorts may proceed simultaneously

• Same subjects may participate in multiple phases

• Subjects who have participated in a phase will not be required to repeat the run-in period if they have already participated in prior phase as per Sponsor discretion.

• When subjects are using Auto Mode with the AHCL system, the automatic basal insulin delivery target should be set to 100 mg/dL.

**Table 1. Summary of Phases for Feasibility 2**

Cohort	Phase	Age	Algorithm	Challenge
A	1	14+	Digital Twin	Manual Mode/ Auto Mode Transition – at home
A	2	2-13	Digital Twin	Manual Mode/ Auto Mode Transition – at home
A	3	14+	Digital Twin	Missed Meal Bolus – at home
A	4	2-13	Digital Twin	Missed Meal Bolus – at home
C	5	14+	Meal Prediction	In Clinic Observation
C	6	2-13	Meal Prediction	In Clinic Observation

### Study Population

For Feasibility 2, the study population will include patients with type 1 diabetes. Ages 14 and up will be enrolled first, followed by the younger age groups.

### Staged Enrollment in all Cohorts

- Enrollment of pediatric subjects 2-13 years of age into a specific phase may not proceed until N=10 subjects 14 years and older have completed the corresponding phase and safety data has been reviewed by the Data Monitoring Committee (DMC).
- Study subjects 2-6 years of age will be enrolled in Cohort A and Cohort C only after completing an in clinic observational study using the AHCL system. See details about the observational study procedures below.

## **Study Procedures:**

### **General:**

All subjects will be trained on diabetes management principles, such as the treatment of hyperglycemia and hypoglycemia. In addition, there will be training regarding the need to have access to oral glucose and glucagon in case of hypoglycemia. Subjects will be asked to continue performing routine self-monitoring of blood glucose (SMBG) checks, as they were doing prior to enrolling in the study. For study purposes, subjects will be instructed to perform SMBG if they are experiencing a severe hyperglycemic event or Diabetic Ketoacidosis (DKA). Please note: If a subject has a severe hypoglycemic event, subject should attempt to retrieve SMBG result from person providing assistance. As a precaution, subjects will be told that they should keep their own insulin pump supplies in a safe place and to have back up supplies on hand (such as insulin and syringe) in the event they are asked to revert back to their own therapy during the study or experience study pump issues (i.e. infusion set occlusion with high glucose).

Subjects will be instructed to insert glucose sensors only in the locations that are specified in the User Guide materials.

### **SMBG recommendations:**

Typically, SMBG is required for calibration. Occasionally, subjects may receive a notification if the pump needs a BG to enter or stay in Auto Mode. For study purposes, subjects will be instructed to perform SMBG if they are feeling low (but sensor glucose [SG] is not low) and treat as needed. They should also perform SMBG if they are experiencing a severe hyperglycemic event or DKA. Please note: If a subject has a severe hypoglycemic event, subject should attempt to retrieve a SMBG result from the person providing assistance. If SMBG is required for monitoring, it will be detailed in the visit study procedures.

## **FEASIBILITY 2**

Subjects who participated in [REDACTED] will complete Visit 10, where they will choose to either participate in Feasibility 2 or exit the study.

### **Cohort A: Insulin Delivery Recommendations Derived from the Digital Twin Algorithm**

The Digital Twin algorithm resides in the Medtronic Data Cloud. By wearing the system during the run-in period, the patient starts to accumulate device data that will be uploaded to CareLink™ after 3 full weeks (22 midnights). The algorithm will then calculate individualized insulin delivery recommendations that will be made available to the investigator.

### **Digital Twin Challenge #1: Alternating Between Auto Mode & Manual Mode**

**Purpose:** The purpose of this challenge is to observe subject safety when subjects frequently exit Auto Mode and transition back and forth between Auto Mode and Manual Mode. The purpose of this data collection is also to assist in the development of the Digital twin algorithm.

**Rationale:** Patients sometimes intentionally switch from Auto Mode to Manual Mode for brief periods of time depending on their circumstances.

### **Run-in Period for Digital Twin Challenge #1**

At the conclusion of the run-in period, insulin delivery recommendations (i.e., insulin carbohydrate ratio, basal rate changes, insulin sensitivity and active insulin time) will be calculated by the cloud-based Digital Twin algorithm based on uploaded CareLink™ data.

### **Run-in Period Study Procedures Based on Therapy at Screening**

- Patients who come in using pump with CGM at Screening will spend a minimum of 30 days using the AHCL system during the run-in period. Device settings may be adjusted as needed
- Patients who are using MDI therapy or a pump without CGM (CSII) at Screening will spend at least 2 additional weeks using the AHCL system during the run-in period. Part of the extra time will be used to collect blinded CGM data as a baseline. The rest of the time will be used to allow subjects get used to pump and CGM. Device settings may be adjusted as needed.
- With the AHCL system, the auto basal rate target should be set to 100mg/dL for the duration of the study, unless the investigator considers this setting to be a safety issue for a subject. At the investigator's discretion, the setpoint may be set to 120mg/dL.
- All subjects will be asked to upload the pump and meter weekly during the run-in period.

### **Study Period Procedures for Digital Twin Challenge #1**

Following the run-in period, subjects will participate in a study period lasting approximately 5-6 weeks. For the duration of the study period, subjects will be asked to switch back and forth between Auto Mode and Manual Mode, according to a schedule that will be provided to each site by the Sponsor. Subjects will be instructed to upload the pump and meter at specific time points during the study period. Device settings recommendations will be provided during this study period. Investigators should make every attempt to follow these recommendations, except if they do not agree with the device settings recommendations, based on safety concerns. Investigators may adjust device settings based on safety.

#### **Device Setting changes**

- At the start of the study period, insulin delivery settings based on data collected during the run-in period will be made available to the investigator.

- If the investigator agrees with the new settings, they will be programmed into a subject's study pump.
- If the investigator does not agree with the recommendations, they may be implemented gradually over a period of time, e.g. 1-2 weeks.
- If the investigator does not agree with the recommendations and does not wish to implement them gradually, details about the disagreement will be noted on the applicable CRF.
- After approximately 2 weeks of the study period, following a pump upload by subjects at home, new device settings will be made available.
  - If the investigator agrees with the new settings, they will be programmed into a subject's study pump.
  - If the investigator does not agree with the recommendations, the investigator will enter details about the disagreement on the applicable CRF.
- After approximately 3 weeks of the study period, following a pump upload by subjects at home, new device settings will be made available.
  - If the investigator agrees with the new settings, they will be programmed into a subject's study pump.
  - If the investigator does not agree with the recommendations, the investigator will enter details about the disagreement on the applicable CRF.
- After approximately 4 weeks of the study period, following a pump upload by subjects at home, new device settings will be made available.
  - If the investigator agrees with the new settings, they will be programmed into a subject's study pump.
  - If the investigator does not agree with the recommendations, the investigator will enter details about the disagreement on the applicable CRF.

The table below shows an example of a transition schedule between Auto Mode and Manual Mode; different variations will be provided by the Sponsor to the investigational center. The transitions between Auto Mode and Manual Mode should occur between 7am and 12 Noon.

**Table 2. Example of Manual mode Transitions during the study period - Digital Twin Challenge #1**

Week	Day 1	Day 2	Day 3	Day 4	Day 5	Day 6	Day 7
1	Manual Mode	Auto Mode					

2	Auto Mode	Auto Mode	Manual Mode	Auto Mode	Auto Mode	Auto Mode	Auto Mode
3	Auto Mode	Auto Mode	Auto Mode	Auto Mode	Manual Mode	Auto Mode	Auto Mode
4	Auto Mode	Manual Mode	Auto Mode	Auto Mode	Auto Mode	Auto Mode	Auto Mode
5	Auto Mode	Auto Mode	Auto Mode	Manual Mode	Auto Mode	Auto Mode	Auto Mode

**Digital Twin Challenge #2: Eating a Meal without Giving an Insulin Bolus**

**Purpose:** The challenge is designed to test the post prandial effect of a subject eating a meal without giving an insulin meal bolus. The purpose of this data collection is also to assist in the development of the Digital twin algorithm.

**Rationale:** During routine diabetes management, patients with diabetes may forget to give insulin for their meal. This challenge helps to collect data on how the Digital Twin algorithm will make insulin delivery recommendations in patients who forget to take insulin with their meal.

**Run-in Period for Digital Twin Challenge #2**

At the conclusion of the run-in period, insulin delivery recommendations (i.e. insulin carbohydrate ratio, basal rate changes, insulin sensitivity and active insulin time) will be calculated by the cloud-based Digital Twin algorithm based on uploaded CareLink™ data.

**Run-in Period Study Procedures Based on Therapy at Screening**

- Patients who come in using pump with CGM at Screening will spend a minimum of 30 days using the AHCL system during the run-in period. Device settings may be adjusted as needed
- Patients who are using MDI therapy or pump without CGM (CSII) at Screening will spend at least 2 additional weeks using the AHCL system during the run-in period. Part of the extra time will be used to collect blinded CGM data as a baseline. The rest of the time will be used to allow subjects get used to pump and CGM. Device settings may be adjusted as needed.
- With the AHCL system, the auto basal rate target should be set to 100mg/dL for the duration of the study, unless the investigator considers this setting to be a safety issue for a subject. At the investigator's discretion, the setpoint may be set to 120mg/dL.
- All subjects will purposely withhold insulin at either breakfast or lunch on each day of the run-in period (approximately 23 days)
- Subjects will check their blood glucose at the start of the missed bolus meal as well as 2 hours after the start of the meal; they will give correction insulin as needed. Confirmation of BG is entered on an electronic log

- Subjects will record the calculated CHO on an electronic log, because it is not entered into the Bolus Wizard
- Subjects will be asked to upload their pumps and meters weekly

### **Study Period for Digital Twin Challenge #2 (at study site selected by Sponsor)**

Following the run-in period, subjects will participate in a study period lasting approximately 5-6 weeks. Subjects will be divided into separate groups:

**Group 1:** Approximately 50% of subjects will purposely withhold insulin for either Breakfast or lunch on each day during weeks 1 through 3. The amount of CHO will be collected on a log, because it is not entered into the Bolus Wizard. Subjects will also check their glucose at the start of the meal as well as 2 hours after the start of the meal and give correction insulin as needed. For the remainder of the study, i.e. weeks 4 and 5, subjects in this group will give standard insulin at all meals.

[figure not shown]
**Group 2:** Approximately 50% of subjects will give standard insulin at all meals for the duration of the study period. CHO data will be collected directly from subject's data entry into the pump through CareLink™.

Subjects will be instructed to upload the pump and meter at specific time points during the study period. Device settings recommendations will be provided during this study period. Investigators should make every attempt to follow these recommendations, except if they do not agree with the device settings recommendations, based on safety concerns. Investigators may adjust device settings based on safety.

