#### **Device Setting**

- At the start of the study period, insulin delivery settings based on data collected during the run-in period will be made available to the investigator.
  - If the investigator agrees with the new settings, they will be programmed into a subject's study pump.
  - If the investigator does not agree with the recommendations, they may be implemented gradually over a period of time, e.g. 1-2 weeks.
  - If the investigator does not agree with the recommendations and does not wish to implement them gradually, details about the disagreement will be noted on the applicable CRF
- After approximately 2 weeks of the study period, following a pump upload by subjects at home, new device settings will be made available.
  - If the investigator agrees with the new settings, they will be programmed into a subject's study pump.
  - If the investigator does not agree with the recommendations, the investigator will enter details about the disagreement on the applicable CRF.
- After approximately 3 weeks of the study period, following a pump upload by subjects at home, new device settings will be made available.
  - If the investigator agrees with the new settings, they will be programmed into a subject's study pump.

- If the investigator does not agree with the recommendations, the investigator will enter details about the disagreement on the applicable CRF
- After approximately 4 weeks of the study period, following a pump upload by subjects at home, new device settings will be made available.
  - If the investigator agrees with the new settings, they will be programmed into a subject's study pump.
  - If the investigator does not agree with the recommendations, the investigator will enter details about the disagreement on the applicable CRF.

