**Study Period Visits:**

- Visit 11 (Office or Telemedicine): Day 30 (+7 days) after Visit 3
  - Start Study Period
  - Retrieve insulin delivery device settings recommendations
  - Review/approve settings before programming pump (please note that investigator discretion may be used as described above)
  - Review CareLink™ Upload
  - Instruct subjects regarding study procedures for Challenge #2
- Visit 12 (Telephone): Day 1 after Visit 11
  - Review CareLink Upload
- Visit 13 (Telephone): Day 2 after Visit 11
  - Review CareLink™ Upload
- Visit 14 (Telephone): Day 7 (+2) after Visit 11
  - Review CareLink™ Upload
  - Instruct subjects to upload on Day 6 after Visit 14
- Visit 15 (Office or Telephone): Day 8 (+3 days) after Visit 14
  - Review CareLink™ Upload
  - Retrieve insulin delivery device settings recommendations
  - Review/approve settings before programming pump (please note that investigator discretion may be used as described above)
  - Program pump with insulin delivery settings

- Instruct subjects to upload on Day 6 after Visit 15
- Visit 16 (Office or Telemedicine): Day 8 (+3 days) after Visit 15
  - Review CareLink™ Upload
  - Retrieve insulin delivery device settings recommendations
  - Review/approve settings before programming pump (please note that investigator discretion may be used as described above)
  - Program pump with insulin delivery settings
  - Instruct subjects to upload on Day 6 after Visit 16
- Visit 17 (Telephone): Day 8 (+3 days) after Visit 16
  - Review CareLink™ Upload
  - Retrieve insulin delivery device settings recommendations
  - Review/approve settings before programming pump (please note that investigator discretion may be used as described above)
  - Program pump with insulin delivery settings
- Visit 18 (Office or Telemedicine): Day 7(+3 days) after Visit 17
  - Review CareLink™ Upload
  - End of Phase
  - Return AHCL system unless phase is repeated Review CareLink™ Upload

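### Challenge #2 is built to show the effect of a missed meal bolus, but no planned summary separates withheld from bolused meals, Group 1 from Group 2, or weeks 1-3 from later

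*Protocol*

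**What the plan says.** **Aim.** The protocol introduces Digital Twin Challenge #2 with: "The challenge is designed to test the post prandial effect of a subject eating a meal without giving an insulin meal bolus". It adds that the data will also support development of the algorithm. The SAP repeats both statements.

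**Design.** In the run-in, every subject withholds one breakfast or lunch bolus a day. In the study period the subjects divide (Protocol section 5, repeated in the synopsis and SAP section 5):

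- Group 1 continues to withhold one breakfast or lunch bolus daily through week 3. After that: "For the remainder of the study, i.e. weeks 4 and 5, subjects in this group will give standard insulin at all meals".
- For Group 2: "Approximately 50% of subjects will give standard insulin at all meals for the duration of the study period".

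**Meal data.** For Group 1's withheld meals: "The amount of CHO will be collected on a log, because it is not entered into the Bolus Wizard". Group 2's carbohydrate data come from pump entries.

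**Analysis.** Protocol 14.4.3 summarises by phase, and SAP 7.1.3 defines the efficacy set by phase. SAP 7.9.1 lists the sensor glucose metrics and, where applicable, a postprandial analysis over a window of up to 5 hours. The only subgroups it names are Cohort A and Cohort C.

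**The concern.** Groups 1 and 2 sit in the same phase and the same cohort, so neither named summary level tells them apart. The same is true of weeks 1-3 versus later weeks, and of withheld versus bolused meals. The postprandial analysis is where the stated aim would be answered, but it has no split by bolus status and no rule for what counts as a meal.

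In a purely descriptive study the tables are the result, so their strata decide what is learned. Subjects, including children aged 2-13 in Phase 4, deliberately miss boluses for this information. Severe hypoglycemia and DKA are still reported as events; the gap is confined to the sensor glucose and postprandial summaries.

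**Working it through.** The plan gives no figure to reproduce: there is no power, effect size or assumed postprandial difference. The check has two parts.

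**1. Design against summary levels**

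| Contrast created by the design | By phase | By Cohort A/C |
|---|---|---|
| Group 1 vs Group 2 | not separated | not separated |
| Weeks 1-3 vs week 4 onward | not separated | not separated |
| Withheld vs bolused meal | not separated | not separated |

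**2. How far a phase-level postprandial mean is diluted**

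Inputs from the documents:

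- Withheld meals per Group 1 subject in the study period: one a day for 3 weeks = 21. Group 2: 0. The groups are about equal in size.
- Length of study period: 5 weeks = 35 days (SAP). From the Challenge #2 visit schedule, Visit 14 is Day 7 after Visit 11, Visits 15 to 17 follow at 8-day steps (for example "Visit 17 (Telephone): Day 8 (+3 days) after Visit 16"), and Visit 18 is 7 days after Visit 17. That gives 7 + 8 + 8 + 8 + 7 = 38 days.
- Subjects per phase: at least 12-18 (Protocol 14.5), so about 6-9 per group.

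Assumptions not in the documents: 3 or 4 meals a day, and a true rise D of 30, 60 or 100 mg/dL in postprandial mean when the bolus is missed.

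For one Group 1 and one Group 2 subject together, share = 21 / (2 × days × meals per day), and shift in the phase mean = D × share.

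| Days | Meals/day | Share withheld | Shift, D = 30 | D = 60 | D = 100 |
|---|---|---|---|---|---|
| 38 | 3 | 21/228 = 9.2% | 2.8 | 5.5 | 9.2 |
| 35 | 3 | 21/210 = 10.0% | 3.0 | 6.0 | 10.0 |
| 38 | 4 | 21/304 = 6.9% | 2.1 | 4.1 | 6.9 |
| 35 | 4 | 21/280 = 7.5% | 2.25 | 4.5 | 7.5 |

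Variants:

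- If meals are taken from Bolus Wizard entries, the share is 0%, because withheld meals are not entered there.
- At Cohort A level, with Challenge #1 phases of equal size (assumption) and 3 meals a day, it is 21/456 = 4.6%.
- If a 30-day run-in with 23 withheld meals per subject is pooled in, again at 3 meals a day, it is (2 × 23 + 21) / (3 × (2 × 30 + 76)) = 67/408 = 16.4%.

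Within Group 1 in weeks 1-3 the share is 1 in 3 (or 1 in 4) meals; everywhere else in the study period it is zero. Group 1 contributes 6 × 21 = 126 to 9 × 21 = 189 withheld meals per phase in weeks 1-3, so a separate description is feasible.

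**The case against.** **The pooling is inferred.** This is correct. SAP 7.3 pools centres, and no sentence says that Groups 1 and 2 are to be combined. The accurate statement is that no split is specified while a coarser set of subgroups is named. An analyst who follows the text would not produce the contrast.

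**SAP 7.4 puts all available data in listings and tabulations, and 7.9.1 has a postprandial analysis.** A listing does not summarise an effect, and neither section mentions group or bolus status.

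**Meals could be found another way.** Protocol Table 6 says the algorithm can detect unannounced meals. The SAP does not adopt this. If it did, withheld meals would be captured but still averaged with the others.

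**The only formal objective is to collect device data, and the endpoints are descriptive.** Both are true, and they limit the weight of the point. They do not supply a summary for the aim stated for this challenge.

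Four stronger readings are tempting and should not be drawn:

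- *That the two groups isolate the bolus effect.* They do not differ in bolus behaviour alone. For the study period, the glucose checks at meal start and 2 hours, with correction insulin as needed, are written for Group 1 only, and the meal-data source differs. Settings may also diverge inside weeks 1-3: Visit 15 falls at about Day 15 (7 + 8), after an upload at about Day 13 (7 + 6). Besides this, "Investigators may adjust device settings based on safety".
- *That one can calculate the share of study days run on settings learned under the other meal behaviour.* The documents do not give the look-back window for later recommendations.
- *That unannounced meals leave an unmitigated carb-ratio hazard.* Table 6 names the risk but also lists mitigations: meal detection, a check on total daily dose, and physician approval.
- *That the 47-minute criterion for time below 70 mg/dL is distorted.* The documents do not say at what level it applies, nor give a background value.

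**Conclusion.** The omission stands. Under the summaries as specified, the missed-bolus effect is either absent from the postprandial analysis or diluted to about 9-10% of the meals in a phase (3 meals a day) or 7-7.5% (4 meals a day). The planned tables also cannot show whether glucose differs after Group 1 returns to full bolusing. The percentages rest on the assumed meal count, equal groups and nominal dates; the 30-100 mg/dL effects only illustrate dilution. The conclusion does not depend on them, because no specified stratum separates the meals under any of the variants.

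This is a gap in descriptive reporting worth correcting before analysis. It does not affect safety event reporting, sample size, the success criteria or the stopping rules.

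**What to change.** In SAP 7.9.1, for Phases 3 and 4:

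1. State that withheld-bolus meals are identified from the log. Present the postprandial metrics separately for withheld-bolus meals and for bolused breakfasts and lunches. Dinner is never withheld, so it does not belong in the comparison.
2. Report the existing sensor glucose metrics by Group 1/Group 2 and by period (weeks 1-3; week 4 to Visit 18), using each subject's actual dates.
3. Label these results descriptive and say why: about 6-9 subjects per group per phase, no stated randomisation to groups, checks and corrections written for Group 1 only (so the effect shown is with corrections allowed), and settings that may differ between groups from Visit 15.

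The cost is SAP wording and a few table rows, from pump uploads and a log already planned. One practical check is needed: the documents do not say whether the log records meal time. If it does not, the glucose check that Group 1 makes at the start of the withheld meal may serve to date it. A by-subject listing of settings changes and a separate listing of repeated phases are optional additions.
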